5.8 Safety Analyses

For all safety variables, descriptive statistics will be presented by study part, treatment group, and visit (where applicable) using the safety analysis set and randomized withdrawal safety analysis set. In summaries of change from baseline safety variables, only participants with both baseline and change from baseline values will be included. No formal hypothesis testing will be performed for any safety variable.

5.8.1 AEs

The overall incidence of participants having at least one AE in each of the following categories will be summarized by treatment group and dose level, as defined in [Section 5](#):

- Any TEAE
- Any serious adverse event (SAE)
- Any AE leading to death
- Any AESI
- Any TEAE leading to study drug withdrawal
- Any related TEAE

The overall AE incidence summary, as well as summaries identified in subsequent sections, will be reported by part and phase. Part A and Part B open-label titration phase summaries will be based on the safety analysis set. Part B double-blind randomized withdrawal phase summaries will be based on the randomized withdrawal analysis set.

All AE data will be listed by study part and participant. Separate listings will be presented for SAEs, AEs leading to death, and TEAEs leading to study drug withdrawal.

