3.2. Part B

Objective	Endpoint
Primary	

 • To evaluate the safety and tolerability of PRAX-944 in participants with ET 	
 • Incidence and severity of AEs • Changes in vital sign measurements • Changes in clinical laboratory results • Changes in ECG parameters • Incidence of C-SSRS measured suicidal ideation or behavior
Secondary	

 • To evaluate the efficacy of PRAX-944 on upper limb tremor in participants with ET 	
 • Change from Baseline to Day 42 in TETRAS Upper Limb score (bilateral sum of items 4a, 4b, and 4c)

 • To evaluate the efficacy of PRAX-944 on other measures of tremor severity in participants with ET 	
 • Change from Baseline to Day 7 and Day 21 in TETRAS Upper Limb score (bilateral sum of items 4a, 4b, and 4c) • Change from Baseline to Day 7, Day 21, and Day 42 in the following: 
 ○ TETRAS Performance subscale total score ○ Accelerometer-based upper limb score (bilateral sum of items 4a, 4b, and 4c) ○ TETRAS Performance individual item scores

Objective	Endpoint

To evaluate the efficacy of PRAX-944 on measures of disease impact in participants with ET	
Change from Baseline to Day 7, Day 21, and Day 42 in the following:
TETRAS ADL subscale scoreQuality of Life in Essential Tremor Questionnaire (QUEST) total and subscale scores

Exploratory

Objective	Endpoint
	

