3.3 Randomized Withdrawal Safety Analysis Set

The randomized withdrawal safety analysis set includes all participants who received at least 1 dose of blinded study drug in the randomized withdrawal phase of Part B. Participants will be classified according to actual treatment received. The randomized withdrawal safety analysis set will be used for all demographic, baseline characteristics, prior/concomitant medication, study drug exposure, and safety analyses for the randomized withdrawal phase of Part B.

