3.5 Randomized Withdrawal Analysis Set

The randomized withdrawal analysis set is a subset of the full analysis set and includes all participants who were randomized into the double-blind, randomized withdrawal phase of Part B and have a valid Day 42 TETRAS assessment and at least 1 valid TETRAS assessment after Day 42. The randomized withdrawal analysis set will be used for the analysis of all efficacy data collected during the randomized withdrawal phase.

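### SAP 5.8.1 puts the blinded-phase AE tables of Part B on the efficacy set, so a dosed participant without the required TETRAS ratings drops out of a primary safety endpoint

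*SAP*

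**What the plan says.** The SAP has two analysis sets for the randomized withdrawal phase, and their names differ by one word.

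- **Safety set (SAP 3.3).** It takes in "all participants who received at least 1 dose of blinded study drug in the randomized withdrawal phase of Part B". On grouping it says: "Participants will be classified according to actual treatment received". The section assigns this set to the phase's safety analyses.
- **Efficacy set (SAP 3.5).** It is a subset of the full analysis set. It is limited to randomized participants who "have a valid Day 42 TETRAS assessment and at least 1 valid TETRAS assessment after Day 42". Its use is stated: "The randomized withdrawal analysis set will be used for the analysis of all efficacy data collected during the randomized withdrawal phase".

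The general safety section, SAP 5.8, says that every safety variable is summarized "using the safety analysis set and randomized withdrawal safety analysis set".

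The adverse event section, SAP 5.8.1, departs from this: "Part B double-blind randomized withdrawal phase summaries will be based on the randomized withdrawal analysis set". The sentence before it extends the rule to the AE summaries in the sections that follow, so it governs 5.8.1.1 to 5.8.1.4 as well.

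In Protocol 3.2, "Incidence and severity of AEs" is the first endpoint listed under the Part B primary objective.

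**The concern.** As written, 5.8.1 makes a participant's place in the AE tables depend on having tremor ratings. A participant who takes blinded drug, stops because of an adverse event and gives no further valid TETRAS leaves both the numerator and the denominator. So does one with no valid Day 42 TETRAS, even after completing the blinded phase. In the first case exclusion is linked to tolerability, which is what the table is meant to show.

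Two further effects follow from the definitions. Laboratory, vital sign and ECG summaries of the same phase fall under 5.8 and use the safety set, so their denominators can differ from those of the AE tables. And the efficacy set requires randomization but no blinded dose, and has no rule on actual treatment. A participant who was randomized but never took blinded drug, and was rated later, could therefore enter the AE denominator.

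**Working it through.** **Step 1. The two sets side by side.**

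| | Safety set (SAP 3.3) | Efficacy set (SAP 3.5) |
|---|---|---|
| Full analysis set membership | not required | required |
| Blinded dose | at least 1 | not required |
| Valid Day 42 TETRAS | not required | required |
| Valid TETRAS after Day 42 | not required | at least 1 |
| Grouping | actual treatment | not stated |
| Stated use | safety in this phase | efficacy in this phase |
| Named for AEs by | SAP 3.3 and 5.8 | SAP 5.8.1 |

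A participant with at least one blinded dose who lacks either the Day 42 rating or every later rating is in the first set and not in the second.

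**Step 2. Is the departure declared?** No. SAP 7.1 lists the changes from the protocol, and a move of AE tables to an efficacy set is not among them. Protocol 9.2 also bases safety analyses on a set defined by dosing.

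**Step 3. Where do the excluded participant's events go?** SAP 4.10.1 keeps events of the randomized withdrawal phase out of the open-label summaries, and assigns events in safety follow-up to the participant's last phase. The blinded-phase and follow-up events of an excluded participant would therefore normally appear in no summary table. The exception is an event with an imputed onset date that could fall in either phase. All events stay in the listings under 5.8.1.

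**Step 4. The plan's own AE figure.** SAP 2.3 gives an 80% probability of seeing at least one AE of 15% incidence with 10 participants: 1 − 0.85^10 = 0.803. It reproduces, so the same formula serves below.

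**Step 5. Size.** Inputs: about 12 participants in Part B and up to 24 (SAP 2.3), randomized 1:1 (SAP 2.2). If all are randomized, that is 6 or 12 per arm. The documents do not say how many dosed participants will lack a required rating, so one per arm is an assumption, for illustration.

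| One participant lost from the arm | 6 per arm | 12 per arm |
|---|---|---|
| Rate in the safety set, one participant with the event | 1/6 = 16.7% | 1/12 = 8.3% |
| The lost participant had the event | 0/5 = 0% | 0/11 = 0% |
| The lost participant did not have it | 1/5 = 20.0% | 1/11 = 9.1% |
| Chance of at least 1 AE at 15% incidence, safety set | 1 − 0.85^6 = 62.3% | 1 − 0.85^12 = 85.8% |
| Same chance, one fewer | 1 − 0.85^5 = 55.6% | 1 − 0.85^11 = 83.3% |

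The last two rows treat the loss as unrelated to the event. If participants with events are the ones lost, the chance of the table showing the event falls further.

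**The case against.** The strongest reply is that this is a dropped word. The plan states the right rule twice, in 3.3 and 5.8, reserves the other set for efficacy in 3.5, and gives no order of precedence by which 5.8.1 would prevail. That may well explain the error, but it does not correct the text. 5.8.1 is the specific rule for these tables, and the set it names exists, so a programmer following it would meet nothing that fails.

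The route to exclusion is also narrow. Protocol 7.1 keeps participants who stop study drug in the trial for safety and efficacy evaluation. A valid TETRAS at Day 56, Day 70 or early termination meets the later-rating condition, and Day 42 itself has two scheduled assessments. This stands as a limit on size. It does not close the gap: under Protocol 7.2 the early termination visit is held only if possible, and 7.3 provides for loss to follow-up.

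Three more limits stand:

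- The rate falls only if the excluded participant had the event; otherwise it rises. The affected arm could also be placebo.
- The open-label AE tables use the safety analysis set and are unaffected, as are the other safety variables. Only the AE summary tables of the two-week blinded phase are at issue.
- All adverse events are listed, with separate listings for serious events, deaths and events leading to withdrawal of drug. With 12 to 24 participants these can be read in full, and safety is descriptive with no testing.

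**Conclusion.** The concern holds. SAP 5.8.1 contradicts 3.3 and 5.8, and followed literally it applies an efficacy set to part of the Part B primary endpoint. The size cannot be fixed from the documents. It is zero if the two sets turn out to have the same members. If one dosed participant per arm is lost and had the only event of its kind, the arm's rate falls by 16.7 percentage points (6 per arm) or 8.3 (12 per arm). These figures assume that all 12 or 24 participants are randomized, in equal arms.

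The bias is downward when the reason for the missing rating is the adverse event itself; it has no fixed direction otherwise. The loss is confined to summary tables, because the listings keep every event. It should still be corrected before lock: the tables concern a primary endpoint, and SAP 3 fixes set membership before database lock and unblinding.

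**What to change.** In SAP 5.8.1, insert the word safety so that the sentence on the Part B double-blind phase names the randomized withdrawal safety analysis set of section 3.3. Grouping by actual treatment then follows from 3.3. State that the rule covers 5.8.1.1 to 5.8.1.4, and check that the AE table templates use the same set.

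The cost is one word in the SAP and a check of the templates. No further data are needed, and nothing is lost. The counts per analysis set already planned in SAP 5.1 will show whether the two sets differ.

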5.8.1.1 TEAEs

The incidence of TEAEs will be summarized by SOC and preferred term. Each participant will be counted only once per SOC and preferred term. The incidence of TEAEs by preferred term will also be summarized.

5.8.1.2 TEAEs Leading to Study Drug Withdrawal

The incidence of TEAEs leading to study drug withdrawal will be summarized by SOC and preferred term. Each participant will be counted only once per SOC and preferred term.

5.8.1.3 TEAEs Related to Study Drug

The incidence of TEAEs related to study drug will be summarized by SOC and preferred term. Each participant will be counted only once per preferred term.

5.8.1.4 TEAEs by Maximum Severity

The incidence of TEAEs will be summarized by maximum severity, SOC, and preferred term, where Severe > Moderate > Mild. Each participant will be counted only once per preferred term and most severe category reported. If missing, severity will be categorized as Severe for summary purposes.

5.8.2 Laboratory Test Results

Descriptive statistics for all reported and change from baseline values will be summarized by test category, laboratory test, and visit. Only the original assessment for each visit day will contribute to descriptive statistics; repeat or unscheduled assessments will not be included in the calculation of descriptive statistics by visit. All laboratory test results data (including pregnancy test and urine drug screen data and any repeat or unscheduled assessments) will be listed by study part, participant, and visit.

Descriptive statistics for all reported and change from baseline values for KIM-1, urine creatinine, and KIM-1 per urine creatinine ratio will be summarized by test and visit. Results will be listed by study part, participant, and visit.

5.8.3 Vital Sign Results

Descriptive statistics for all reported and change from baseline values will be summarized by visit. Only the original assessment for each timepoint will contribute to these summaries; repeat or unscheduled assessments will not be included in the calculation of descriptive statistics by timepoint. The number and percentage of participants with PCI values at any time will be tabulated by treatment group. Summaries of PCI values will include all assessments regardless of whether an original, repeat, or unscheduled assessment. All vital sign results data will be listed by study part, participant, and visit.

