4 DEFINITION OF STUDY VARIABLES

The following definitions will be used throughout the analysis plan for this study:

Study Day

Study day calculations (ex. study day of an event or a visit) will be defined as follows, assuming non-missing dates:

- Study Day = Date of event – Reference date + 1, when the date of interest occurs on or after the reference date;
- Study Day = Date of event – Reference date, when the date of interest occurs before the reference date;

If either date is missing, study day calculations will not be performed.

For this study, the reference date used will be the treatment start date. Based on the calculations above, there will be no study day zero.

Baseline and Change from Baseline

Unless otherwise specified, the baseline value is defined as the last non-missing value collected prior to receiving first dose of study drug. Values collected after the time of treatment start will be excluded from the calculation of baseline as applicable. Post-baseline values will be defined as those collected after the treatment start date (and time, as applicable).

Change from baseline will be defined as: assessment value – baseline value. Change from baseline values will only be derived for post-baseline assessments.

Randomization Baseline and Change from Randomization

The randomization baseline value, used as the reference value for double-blind randomized withdrawal phase efficacy endpoints, is defined as the Day 42 post-dose value. If the Day 42 post-dose value is unavailable, the randomization baseline value will be considered missing.

Change from randomization will be defined as: assessment value – randomization baseline value. Change from randomization values will only be derived for assessments conducted after the randomized treatment start date (and time, as applicable).

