4.10.3 Vital Sign Results

The following vital sign data will be recorded in the eCRF: assessment date, height, weight, BMI, as well as standing and supine temperature, pulse rate, respiratory rate, supine systolic blood pressure (BP), and diastolic BP. An indicator for whether a repeat assessment was taken (Yes/No) will also be recorded in the eCRF for each assessment.

Change from baseline values to each post-baseline assessment will be calculated for pulse rate, respiratory rate, systolic BP, and diastolic BP. In addition, potentially clinically important flags will be derived for systolic BP, diastolic BP, pulse rate, and respiratory rate (see [Table 1](#)).

Table 1: Potentially Clinically Important Criteria for Vital Sign Results

ECG measure	Lower PCI criterion	Upper PCI criterion
Pulse rate	≤50 bpm	≥130 bpm
Systolic BP	<90 mmHg	>130 mmHg
Diastolic BP	<50 mmHg	>85 mmHg
Change in systolic BP	decrease ≥30 mmHg	increase ≥30 mmHg
Change in diastolic BP	decrease ≥30 mmHg	increase ≥30 mmHg

BP = blood pressure; PCI = potentially clinically important

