5 ANALYSIS METHODS

Analysis will be carried out using SAS® (version 9.4 or newer, SAS Institute Inc, Cary, NC). Templates for the summary tables, figures, and participant data listings will be available separately. Data listings will include all data recorded for all enrolled participants; where captured, data entered for screen failure participants will be flagged in the listings.

For all data displays, separate summaries will be generated for each part and phase (open-label titration and double-blind randomized withdrawal) of the clinical trial.

- Part A: All summaries except those for adverse events will use a single "PRAX-944 Overall" column. Summaries of adverse events will use the following columns: "PRAX-944 20 mg qAM", "PRAX-944 40 mg qAM ", and "PRAX-944 Overall".
- Part B: Summaries of disposition and PK will be presented for all of Part B (i.e., not by phase) and will use a single "PRAX-944" column.
- Part B Open-label Titration: Summaries of demographics, baseline characteristics, medical history, prior and concomitant medications, study drug exposure, efficacy, and all safety except adverse events will include a "PRAX-944 Overall" column. Summaries of adverse events will include columns for "PRAX-944 20 mg qAM", "PRAX-944 40 mg qAM ", "PRAX-944 60 mg qAM ", "PRAX-944 80 mg qAM ", "PRAX-944 100 mg qAM ", "PRAX-944 120 mg qAM ", and "PRAX-944 Overall".
- Part B Randomized Withdrawal: Summaries of demographics, baseline characteristics, medical history, prior and concomitant medications, study drug exposure, efficacy, and all safety except adverse events will include the columns "Placebo" and "PRAX-944" for the randomized withdrawal phase. Summaries of adverse events will include columns for "Placebo" and "PRAX-944".

Descriptive statistics for continuous data will include number of participants (n), mean, standard deviation (SD), median, minimum, and maximum. Summaries of change from baseline variables will include only participants who have both a baseline value and corresponding value at the timepoint of interest. Descriptive statistics for categorical data will include frequency and percentage. Where appropriate, descriptive statistics may be presented with 95% confidence intervals (CIs).

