5.8.4 ECG Results

Descriptive statistics for all reported and change from baseline values will be summarized by visit. Only the original assessment for each visit will contribute to these summaries; repeat or unscheduled assessments will not be included in the calculation of descriptive statistics. The number and percentage of participants with PCI values at any time will be tabulated by treatment group; the number and percentage of participants with abnormal ECG findings will be presented similarly. Summaries of PCI values and abnormal ECG findings will include all assessments regardless of whether an original, repeat, or unscheduled assessment. All ECG results data will be listed by study part, participant, and visit.

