5.8.5 C-SSRS

The C-SSRS will be evaluated based on methods described by Nilsson et al. (2013). The number and percentage of participants with any suicidal ideation and/or suicidal behavior following the first dose of study drug will be tabulated.

For the composite endpoint of suicidal ideation, the number and percent of participants who experience any one of the five suicidal ideation events at least once during dosing through follow-up will be tabulated.

For the composite endpoint of suicidal behavior, the number and percent of participants who experience any one of the five suicidal behavior events at least once during dosing through follow-up will be tabulated.

For the composite endpoint of suicidal ideation or behavior, the number and percent of participants who experience any one of the ten suicidal ideation or behavior events at least once during dosing through follow-up will be tabulated.

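### Potentially clinically important (PCI) vital sign and ECG counts have no post-dose limit, so pre-dose readings that meet an absolute threshold can count in the PRAX-944 columns

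*SAP*

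**What the plan says.** SAP 5.8.3 (Vital Sign Results) states: "The number and percentage of participants with PCI values at any time will be tabulated by treatment group". It then says: "Summaries of PCI values will include all assessments regardless of whether an original, repeat, or unscheduled assessment". SAP 5.8.4 (ECG Results) applies the same any-time window and adds abnormal findings: "Summaries of PCI values and abnormal ECG findings will include all assessments regardless of whether an original, repeat, or unscheduled assessment".

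The flag definitions do not supply a window. SAP 4.10.3 says that "potentially clinically important flags will be derived for systolic BP, diastolic BP, pulse rate, and respiratory rate", and 4.10.4 is similar for ECG. Tables 1 and 2 set absolute cut-offs (pulse or heart rate, systolic and diastolic BP, PR, QRS, QT, QTcB, QTcF) and change cut-offs (systolic and diastolic BP, QTcB, QTcF).

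Three other provisions bear on the point:

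- SAP 4 defines post-baseline values and adds: "Change from baseline values will only be derived for post-baseline assessments". Sections 5.8.3 and 5.8.4 do not use the post-baseline term for the PCI counts.
- SAP 5 requires that "separate summaries will be generated for each part and phase", with Placebo columns only in the Part B withdrawal displays.
- SAP 5.8.5 limits the C-SSRS count to participants "with any suicidal ideation and/or suicidal behavior following the first dose of study drug". SAP 4.10.1 limits TEAEs in the same way and allocates AEs to phases in Part B.

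**The concern.** Pre-dose vital signs and ECGs are scheduled in both parts. Several absolute cut-offs, such as systolic above 130 mmHg, diastolic above 85 mmHg, PR of 180 msec or more and QRS of 100 msec or more, can be met by an untreated participant. A programmer who follows 5.8.3 and 5.8.4 literally would count that participant under PRAX-944.

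Changes in vital signs and ECG parameters are among the Part B primary endpoints. Safety is summarized without testing, so a reader will judge these tables by eye. With about 12 participants in a part, one participant moves a percentage by 1/12 = 8.3 points. In a withdrawal arm of about 6 the step is 1/6 = 16.7 points.

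The withdrawal tables raise a second question. The randomized withdrawal safety analysis set (SAP 3.3) selects participants, not assessments. AEs and concomitant medications have explicit phase rules (SAP 4.10.1 and 4.7); vital signs and ECGs have none.

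**Working it through.** The documents give no PCI figure to reproduce. The check therefore has a textual part and an illustration.

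**1. Which criteria are exposed.** A change from baseline is derived only after baseline, so a pre-dose reading cannot meet a change criterion. Absolute criteria and abnormal ECG findings carry no such limit and are exposed.

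**2. How many scheduled readings are pre-dose** (protocol Tables 2 and 3, taking Baseline ECGs as pre-dose).

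| Display | Pre-dose | Post-dose | Pre-dose share |
|---|---|---|---|
| Part A vital signs | Screening, Baseline | Day 1 at 2 h and 6 h, Days 7, 14, 21 | 2 of 7 |
| Part A ECG visits | Screening, Baseline | Days 7, 14 | 2 of 4 |
| Part B vital signs to Day 42 | Screening, Day 1 pre-dose | Day 1 at 2 h and 6 h, Days 7, 21, 42 | 2 of 7 |
| Part B ECG visits to Day 42 | Screening, Baseline | Days 7, 21, 42 | 2 of 5 |

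Screening ECGs are triplicate. By tracing, the ECG shares are 4 of 6 and 4 of 7.

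**3. Size for systolic BP, Part B open-label schedule.** All distributional inputs are assumptions: mean m = 120 to 130 mmHg, SD s = 12 to 15 mmHg, normal readings, within-person correlation 0.6, no drug effect. Let a = (130 − m)/s. The chance that k readings are all at or below 130 is

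L(k) = ∫ Φ((a − √0.6·z)/√0.4)^k φ(z) dz.

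With p positions per timepoint (1 = supine only, 2 = supine and standing):

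- any time = 1 − L(7p)
- post-dose only = 1 − L(5p)
- excess = L(5p) − L(7p)
- newly high, no high pre-dose reading at all = L(2p) − L(7p)
- newly high, not high at the last pre-dose timepoint = L(p) − L(6p)

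| Positions | Mean / SD | Any time | Post-dose only | Excess | New vs all pre-dose | New vs last pre-dose |
|---|---|---|---|---|---|---|
| Supine | 120 / 12 | 50.8% | 45.4% | 5.4 | 20.4% | 28.1% |
| Supine | 120 / 15 | 58.4% | 52.9% | 5.5 | 21.5% | 30.7% |
| Supine | 125 / 12 | 69.2% | 63.9% | 5.2 | 21.9% | 33.0% |
| Supine | 125 / 15 | 72.5% | 67.4% | 5.0 | 21.6% | 33.3% |
| Supine | 130 / 12 or 15 | 83.7% | 79.7% | 4.0 | 19.0% | 32.0% |
| Both | 120 / 12 | 61.1% | 56.3% | 4.9 | 19.4% | 28.6% |
| Both | 120 / 15 | 68.4% | 63.8% | 4.6 | 19.3% | 29.5% |
| Both | 125 / 12 | 78.1% | 74.1% | 4.0 | 17.9% | 29.0% |
| Both | 125 / 15 | 80.9% | 77.1% | 3.8 | 17.2% | 28.4% |
| Both | 130 / 12 or 15 | 89.8% | 87.2% | 2.6 | 13.2% | 23.9% |

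The excess is 2.6 to 5.5 points, or 0.3 to 0.7 of 12 participants. Both position counts are shown because the protocol measures blood pressure supine and standing, while SAP 4.10.3 names only supine systolic explicitly.

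**4. ECG.** There are fewer post-dose visits, so the excess may be larger. Let q be an assumed chance of 5 to 30% per visit of meeting a cut-off without drug effect. If readings were independent, P = 1 − (1 − q)^k gives these ranges:

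- Part A: 18.5 to 76.0% any time (k = 4), against 9.8 to 51.0% post-dose (k = 2).
- Part B open-label: 22.6 to 83.2% (k = 5), against 14.3 to 65.7% (k = 3).

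Independence overstates the excess, because a person's PR or QRS is similar from visit to visit. These are outer figures, not estimates.

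**The case against.** The best defence is that the SAP never says pre-dose readings count. The sentence before the PCI rule in 5.8.3 describes summaries by timepoint, so the any-time wording may only mean pooled over timepoints. That is a fair reading. It leaves the window unstated, and nothing elsewhere closes it.

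The tables are also not the only view of the data. Change criteria cannot be met before dosing, change from baseline is summarized by visit, and every value is listed. This stands and limits the harm to the absolute-threshold and abnormal-ECG counts.

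Three stronger readings are tempting and not supported:

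- A reader might infer that pre-dose or open-label readings will be reported under Placebo. Displays are separated by phase, and the SAP brings open-label results into withdrawal displays explicitly only for efficacy (5.7). What remains is an ambiguity about which readings belong to the phase.
- A reader might take the share with any high pre-dose systolic (42 to 77% over four readings, 30 to 65% over two, same assumptions) as the overcount. Most of those participants would exceed 130 after dosing anyway. The overcount is the excess in the working.
- A reader might infer that the SAP limits all AE counts to the period after first dose. It does so for TEAEs. The overview in 5.8.1 also lists SAEs, AEs leading to death and AESIs without that qualifier.

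**Conclusion.** The point holds for absolute-threshold PCI counts and abnormal ECG findings in the PRAX-944 columns of Part A and Part B open-label titration. It does not reach the change-based criteria. For the withdrawal tables it is an ambiguity only.

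For systolic BP the missing date limit adds about 3 to 6 points. The larger weakness is that even a post-dose count is dominated by people who were already high: 45 to 87% are counted post-dose, but only 13 to 22% are high after dosing with no high pre-dose reading. If only the last pre-dose timepoint is the reference, the newly high share is 24 to 33%. Neither share is zero without a drug effect, because each participant has five post-dose timepoints.

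These sizes rest on the assumed mean, SD, correlation and normality; the documents give none of them. The textual finding does not depend on them.

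**What to change.** In SAP 5.8.3 and 5.8.4:

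- Count PCI values and abnormal ECG findings only from assessments after the first dose of study drug (Part A, open-label titration) or after the first randomized dose (withdrawal phase). Keep repeat and unscheduled assessments in.
- Add a row for participants who newly meet each criterion, and show those already meeting it at baseline in a separate row. State the reference, since the working shows that the choice between the SAP 4 baseline (last value before first dose) and all pre-dose readings changes the count.
- For the withdrawal phase, define the safety baseline as the last value before the first randomized dose. SAP 4 defines a randomization baseline for efficacy endpoints only.
- Leave the thresholds as they are.

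The cost is SAP wording, one added definition and a small amount of programming, with no new data. The drawback is smaller denominators in the new row. If half of 12 participants were above 130 at baseline, which is the single-reading share at an assumed mean of 130, 6 would remain, and in an arm of 6 only 3. Show counts with their denominators.
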